6.1 Management of Nivolumab-Related Adverse Events

Management algorithms for the following nivolumab-related AEs are located in Appendix G – gastrointestinal, renal, pulmonary, hepatic, endocrinopathy, skin, and neurological.

6.1.1 Management of Infusion-Related Reactions

Nivolumab can cause severe infusion reactions, which have been reported in less than 1% of patients in clinical trials. Discontinue nivolumab in patients with Grade 3 or 4 infusion

CONFIDENTIAL

STUDY DRUG: NIVOLUMAB

SARAH CANNON DEVELOPMENT INNOVATIONS STUDY NUMBER:

FINAL PROTOCOL DATE: 07 FEB 2020

BMT 24

VERSION 7

reactions. Interrupt or slow the rate of infusion in patients with Grade 1 or 2 infusion reactions. For management of infusion-related side effects, refer to institutional guidelines.

7. STUDY ASSESSMENTS AND EVALUATIONS

7.1 Overview

All patients should visit the study center on the days specified within this protocol. The complete Schedule of Assessments for this study is shown in Appendix E. The baseline physical examination, medical history, ECOG PS, complete blood count (CBC) with differential and platelets, comprehensive metabolic profile (CMP), and prothrombin time (PT)/partial thromboplastin time (PTT)/International Normalized Ratio (INR) should be done ≤ 7 days prior to initiation of treatment. A pregnancy test must be performed within 72 hours of Cycle 1 Day 1. PET-CT scans should be performed ≤ 6 weeks prior to initiation of treatment. ECG and research samples should be performed ≤ 28 days prior to initiation of study treatment.

7.2 Baseline Study Assessments

The following information will be collected and procedures will be performed for each patient at screening:

- Written informed consent prior to any other study-related procedures (≤ 28 days prior to initiation of treatment)
- Medical history
 - Prior systemic therapy and radiotherapy for HL
 - Results of pre-transplant PET-CT (if done)
- Physical examination, measurements of height (first visit), weight, and vital signs (resting heart rate, BP, respiratory rate, and oral temperature)
- ECOG performance status (see Appendix A)
- 12-lead ECG
- Concomitant medication review
- CBC with 3-part differential and platelets
- CMP to include: glucose, blood urea nitrogen (BUN), creatinine, sodium, potassium, chloride, calcium, carbon dioxide (CO₂), alkaline phosphatase (ALP), AST, ALT, total bilirubin, total protein, and albumin
- Coagulation analysis: PT/INR/PTT
- Serum or urine pregnancy test (must be performed within 72 hours of Cycle 1 Day 1)
- PET-CT scans ≤ 6 weeks prior to initiation of study treatment

CONFIDENTIAL

STUDY DRUG: NIVOLUMAB

SARAH CANNON DEVELOPMENT INNOVATIONS STUDY NUMBER:

FINAL PROTOCOL DATE: 07 FEB 2020

BMT 24

VERSION 7

- Bone marrow biopsy, only if there is prior evidence of bone marrow involvement. If bone marrow biopsy needs to be repeated, it should be done ≤ 28 days prior to initiation of study treatment.

7.3 Study Treatment Assessments

7.3.1 Day 1 of Each Cycle (± 2 days as long as interval between doses is 12-16 days)

- Physical examination, including measurement of weight and vital signs
- ECOG performance status
- AE assessment
- Concomitant medication review
- CBC, including 3-part differential and platelets
- CMP
- Pre-dose research blood sample for correlative analysis (**Cycle 1 Day 1, Cycle 2 Day 1, and Cycle 3 Day 1 only**)

7.4 End of Study Treatment

After withdrawal from or completion of protocol treatment, patients must be followed for AEs for 100 calendar days after the last dose of study drug. The following assessments will be performed:

- Physical examination, including measurement of weight and vital signs
- ECOG performance status
- AE assessment
- Concomitant medication review
- CBC, including 3-part differential and platelets
- CMP
- Serum or urine pregnancy test
- Research blood sample for correlative analysis

7.5 Response Assessment

Patients should have PET-CT scans done per institution standard of care. PET-CT scans are required 1-3 months post-ASCT prior to initiation of therapy, 6 months post-ASCT, and 1 year post-ASCT. If there is prior evidence of bone marrow involvement, patients should also have bone marrow biopsy performed if in CR at these staging visits to document response.

Patients discontinuing therapy early receiving >6 cycles with measurable disease at baseline are recommended to have an EOT PET-CT. Patients ending treatment early need to have a PET-CT at 1 year post-ASCT unless patient progresses or starts a new therapy.

CONFIDENTIAL

STUDY DRUG: NIVOLUMAB

SARAH CANNON DEVELOPMENT INNOVATIONS STUDY NUMBER:

FINAL PROTOCOL DATE: 07 FEB 2020

BMT 24

VERSION 7

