5.3.2 Prohibited Concomitant Medications

The following treatments are prohibited for patients receiving study drug while in this study:

- No other investigational therapy should be given to patients. No anticancer agents other than the study medications should be given to patients. If such agents are required for a patient, then the patient must first be withdrawn from the study.
- Immunosuppressive agents (except to treat a drug-related AE)
- Immunosuppressive doses of systemic corticosteroids (except as stated in Section 5.3.1)

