7.6 Follow-up

Patients will be followed every month (± 1 week) for 3 months and then every 3 months thereafter from the date of last dose of nivolumab for up to 2 years. A research blood sample will be taken 1 year after the first dose of nivolumab. A phone call may be used to assess survival and to record initiation of an alternative form of treatment for lymphoma after response assessment at 1 year post-ASCT.

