10.2 Sample Size Considerations

The null hypothesis to be tested is that the true 12-month PFS is 50% against a two-sided alternative hypothesis of a 70% PFS rate. The 50% 6-month PFS rate was obtained from the Recommendations for Initial Evaluation, Staging, and Response Assessment of Hodgkin and Non-Hodgkin Lymphoma: The Lugano Classification (Cheson et al. 2014, see Appendix F). A two-sided, one-sample log-rank test calculated from a sample of 36 evaluable subjects achieves 80.3% power at a 0.050 significance level to detect an improvement of 20% in 12-month PFS.

The probability that a subject experiences an event during the study is 0.4579. The expected number of events during the study is 16. It is assumed that the survival time distributions of both groups are approximated reasonably well by the Weibull distribution with a shape parameter of 1.00. These proportions assume an enrollment period of 18 months and a follow-up period of 12 months after the last subject is added. In order to allow for a 10% dropout rate, a total of 40 patients will be enrolled. The sample size was calculated using PASS version 14.

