10.4.2 Efficacy Analysis

The primary efficacy analysis will be performed using the FAS. Sensitivity analyses will be performed using the Efficacy-Evaluable Population (EFF).

- Progression-Free Survival (PFS), defined as the time from the first day of study drug administration (Day 1) to disease progression as defined by the Recommendations for Initial Evaluation, Staging, and Response Assessment of Hodgkin and Non-Hodgkin Lymphoma: The Lugano Classification (Cheson et al. 2014, see Appendix F), or death on study. Patients who are alive and free from disease progression will be censored at the date of last tumor assessment.

For PFS Kaplan-Meier curves will be generated and the median time to event and the associated 95% CI be provided. Kaplan-Meier estimates will also be produced for the following specified time points: 12 months and 24 months. The hazard ratio and the 95% CI for these endpoints between the two treatment groups will be calculated.

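### The PFS definition is silent on new anti-lymphoma therapy started before documented progression; the general censoring rule then applies and may bias the single-arm 12-month PFS upward

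*Combined protocol and SAP*

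**What the plan says.** - **PFS (10.4.2).** Time runs from the first dose to Lugano progression or death on study. The one censoring rule is: "Patients who are alive and free from disease progression will be censored at the date of last tumor assessment". New therapy is neither an event nor a named reason for censoring. The only planned sensitivity analysis repeats the analysis in patients who received at least two cycles.
- **Other anticancer agents (5.3.2).** "If such agents are required for a patient, then the patient must first be withdrawn from the study".
- **Scans (7.5, 9 and Appendix E footnote i).** Progression is assessed at 6 months and 1 year after transplant, and other PET-CT scans follow institutional practice. A patient who ends treatment early still needs the 1-year scan "unless patient progresses or starts a new therapy".
- **Follow-up (7.6).** Patients are followed for up to 2 years from the last dose. Telephone contact is allowed for survival status, and its second stated purpose is: "to record initiation of an alternative form of treatment for lymphoma after response assessment at 1 year post-ASCT".
- **Hypothesis (10.2).** "The null hypothesis to be tested is that the true 12-month PFS is 50"%. The alternative is 70%, two-sided.
- **Final analysis (10.5.1).** It waits for every enrolled subject's 12-month disease assessment, which does not fit a scan that some patients are excused.

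**The concern.** Kaplan-Meier and log-rank methods assume that a censored patient has the same future risk as those still under observation. A patient given new lymphoma treatment because relapse is suspected probably does not. If Lugano progression was not documented first, the general rule treats that patient as progression-free at the last scan and drops a likely failure from the curve.

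The opposite path is also open. If a standard-of-care scan is done after the switch, nothing in 10.4.2 stops it from being used, and disease control due to the new therapy would be credited to nivolumab. One patient can follow only one of these paths, but both raise the estimate.

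PFS is the only efficacy endpoint and carries the only formal hypothesis. With a fixed null and no randomized comparator, no second arm shares the bias.

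**Working it through.** **1. The plan's own figure.** Section 10.2 states: "sample of 36 evaluable subjects achieves 80.3% power at a 0.050 significance level", for "A two-sided, one-sample log-rank test", with exponential survival, 18 months of accrual and 12 months of further follow-up.
- Monthly hazards: λ0 = −ln(0.5)/12 = 0.05776 and λ1 = −ln(0.7)/12 = 0.02972.
- Event probability under the alternative: 1 − (0.7 − 0.7^2.5)/(18 × 0.02972) = 0.4579, as stated. Expected events: 36 × 0.4579 = 16.5 (stated 16).
- Null-expected events per patient under the alternative: 0.4579 × 0.05776/0.02972 = 0.8898. Difference from observed: 0.8898 − 0.4579 = 0.4320.
- With test statistic (O − E)/√E and exact variance 0.757 under the alternative, power = Φ[(6 × 0.4320 − 1.96 × √0.8898)/√0.757] = Φ(0.854) = 80.3%, as stated.

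The design reproduces. It allows for no informative censoring.

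**2. Tracing one patient.** The patient stops nivolumab before the planned end, relapse is suspected, and other treatment starts before Lugano progression is documented.
- 5.3.2: withdrawn from the study.
- 7.5: the 1-year PET-CT is no longer required.
- 10.4.2: no event, so censored at the last tumor assessment.

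The PFS clock starts at first dose, 45 to 180 days after transplant, while scans are timed from transplant. For a patient who starts near day 180, the 6-month scan falls at about Day 1, so censoring there keeps almost no follow-up.

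**3. Size in expectation.** The documents give no switching rate. Assume that a fraction f of true progressors switch before documentation and are censored at the last clean scan. For simplicity, put scans at 0, 6 and 12 months on the PFS clock, with exponential survival. With s = √S, where S is the true 12-month PFS, each 6-month interval has apparent survival s/[1 − f(1 − s)], so apparent 12-month PFS = {s/[1 − f(1 − s)]}².

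| True PFS | f = 10% | f = 20% | f = 30% |
|---|---|---|---|
| 50% (s = 0.7071) | 53.1% | 56.4% | 60.1% |
| 70% (s = 0.8367) | 72.3% | 74.8% | 77.4% |

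Example: S = 0.70 and f = 0.30 give 0.8367/(1 − 0.30 × 0.1633) = 0.8798, and 0.8798² = 0.774. Among the 35 patients planned for study drug, switchers by 12 months number 35 × (1 − S) × f: about 1.8 to 5.3 at a true 50%, and 1.1 to 3.2 at a true 70%.

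**4. The same in whole patients.** Take 35 patients with 10 failures by 12 months, 5 of them after the 6-month scan. True PFS is 25/35 = 71.4%. If k of the 5 later failures are censored at the 6-month scan, the estimate is (30/35) × 25/(30 − k): 73.9%, 76.5%, 79.4% and 82.4% for k = 1 to 4. The upper end is extreme, since k = 4 means that 80% of later failures switch undocumented.

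**5. Effect on the test.** In 20,000 simulated trials of 36 patients at a true 50%, the chance of a significant result in nivolumab's favour is 1.8% without switching and 5.1%, 10.7% or 22.5% with f = 10%, 20% or 30%. Mean observed events fall from 24.8 to 22.3, 19.9 and 17.4. The simulation assumes 6-monthly scans beyond month 12, which the plan does not require. Counting the switch as an event returns the chance to 1.5% to 1.8%. That is by construction, because the model places the event at the time of failure.

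**The case against.** Several stronger readings are tempting, and the documents do not support them.

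- **That the plan has a rule censoring patients at new therapy.** It has none. Their censoring follows from the general rule; new therapy itself is left unaddressed.
- **That every switcher is excused the 1-year scan.** The waiver covers only patients who end treatment early. Someone who completes treatment and then switches is not named in it.
- **That withdrawal ends follow-up.** Section 5.3.2 can be read so, but section 6 uses the same expression for patients who are then observed until toxicity resolves, and 7.6 continues follow-up. The text is ambiguous. If withdrawal does end follow-up, the limit to deaths on study could also lose later deaths, which pushes the same way.
- **That PFS will be overstated.** Standard-of-care scans may document Lugano progression before new therapy, and those patients are proper events. Bias needs switching that is both undocumented and related to prognosis. Where switching is unrelated to prognosis, censoring does little harm.
- **That cutting PFS off at new therapy cures the problem.** It does not. A patient already censored at the 6-month scan stays censored there, and the figures in step 4 are unchanged.

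It is also fair to say that PFS is secondary to safety here, that the power calculation does not depend on this point, and that steps 3 and 4 simplify the clock. These points limit the certainty and size of the concern. They leave the gap in 10.4.2, and the likely direction when therapy is started for suspected relapse, in place.

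**Conclusion.** The concern holds as a gap whose default handling may favour the drug. Followed as written, 10.4.2 censors as progression-free a patient who starts new anti-lymphoma therapy without documented progression; 5.3.2 and, for early discontinuers, 7.5 make later documentation less likely. The planned sensitivity analysis does not address this.

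The size cannot be derived from the documents. Under the assumed 10% to 30% undocumented switching among progressors, the upward shift is about 2.3 to 7.4 points at a true 70% and 3.1 to 10.1 points at a true 50%. It approaches zero if switching is unrelated to prognosis or if progression is nearly always documented first. This should be settled before analysis; it does not invalidate the design.

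**What to change.** 1. **Section 10.4.2, sensitivity analysis.** Pre-specify an analysis of 12-month PFS in which the start of new anti-lymphoma therapy before documented progression is an event at its start date. Report it beside the main estimate, with the number of such patients, and draw the efficacy conclusion in light of both.
2. **Section 10.4.2, main analysis.** State that scans taken after the start of new anti-lymphoma therapy are not used. This stops the new therapy's effect being credited to nivolumab. Say in the text that the cut-off alone does not remove the informative censoring, which is why item 1 is needed.
3. **Follow-up and data.** Reconcile 5.3.2 with 7.6 so that these patients remain in follow-up for progression and survival. Confirm that the eCRF captures the start date of new therapy before as well as after the 1-year assessment, since the wording in 7.6 refers to the period after it.

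The cost is one extra analysis, a small wording amendment, and a sensitivity estimate that may be less favourable. These changes concern follow-up and analysis only and alter no treatment rule.

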7.6 Follow-up

Patients will be followed every month (± 1 week) for 3 months and then every 3 months thereafter from the date of last dose of nivolumab for up to 2 years. A research blood sample will be taken 1 year after the first dose of nivolumab. A phone call may be used to assess survival and to record initiation of an alternative form of treatment for lymphoma after response assessment at 1 year post-ASCT.

8. DRUG FORMULATION, AVAILABILITY, ADMINISTRATION, AND TOXICITY INFORMATION

8.1 Nivolumab

Investigational Product	Dosage Form and Strength	Manufacturer
Nivolumab	100 mg/10 mL (10 mg/mL)	Bristol-Myers Squibb

8.1.1 Labeling, Packaging, Supply, and Storage

Nivolumab will be supplied in 10-cc type I flint glass vials with butyl rubber stoppers and sealed with aluminum seals by Bristol-Myers Squibb.

Store under refrigeration at 2°C to 8°C (36°F to 46°F). Protect from light by storing in the original package until time of use. Do not freeze or shake.

All study drugs must be kept in a secure place under appropriate storage conditions. Storage conditions for nivolumab are included on the investigational product label.

Sarah Cannon Development Innovations must be granted access on reasonable request to check drug storage, dispensing procedures, and accountability records.

8.1.2 Preparation and Administration of Nivolumab

Nivolumab is administered as an IV infusion over 60 minutes.

Preparation and administration instructions will be provided in the nivolumab Investigator's Brochure (IB).

8.1.3 Precautions and Risks Associated with Nivolumab

Precautions and risks are located in the nivolumab IB. Management of nivolumab-related AEs is provided in Appendix G.

8.2 Accountability for All Study Drugs

The Principal Investigator (PI, or designee) is responsible for accountability of all used and unused study drug supplies at the site.

CONFIDENTIAL

STUDY DRUG: NIVOLUMAB

SARAH CANNON DEVELOPMENT INNOVATIONS STUDY NUMBER:

FINAL PROTOCOL DATE: 07 FEB 2020

BMT 24

VERSION 7

All study drug inventories must be made available for inspection by the Sponsor or its representatives and regulatory agency inspectors upon request.

At the end of the study, all Sarah Cannon Development Innovations Drug Accountability Record Form(s) will be completed by the site and sent to the Sarah Cannon Development Innovations Regulatory Department. Study drug supplies must not be destroyed unless prior approval has been granted by the Sponsor or its representative. Please contact Sarah Cannon Development Innovations regarding disposal of any study drug.

9. RESPONSE EVALUATIONS AND MEASUREMENTS

Lymphoma progression will be assessed using the Recommendations for Initial Evaluation, Staging, and Response Assessment of Hodgkin and Non-Hodgkin Lymphoma: The Lugano Classification (Cheson et al. 2014, see Appendix F). Progression will be assessed 6 months post-ASCT and 1 year post-ASCT.

10. STATISTICAL CONSIDERATIONS

10.1 Statistical Design

This is a multicenter, open-label, Phase II study of nivolumab as maintenance therapy after ASCT in patients with HL at risk of relapse or progression. The primary, secondary and exploratory objectives and endpoints are found in Section 2.

10.2 Sample Size Considerations

The null hypothesis to be tested is that the true 12-month PFS is 50% against a two-sided alternative hypothesis of a 70% PFS rate. The 50% 6-month PFS rate was obtained from the Recommendations for Initial Evaluation, Staging, and Response Assessment of Hodgkin and Non-Hodgkin Lymphoma: The Lugano Classification (Cheson et al. 2014, see Appendix F). A two-sided, one-sample log-rank test calculated from a sample of 36 evaluable subjects achieves 80.3% power at a 0.050 significance level to detect an improvement of 20% in 12-month PFS.

The probability that a subject experiences an event during the study is 0.4579. The expected number of events during the study is 16. It is assumed that the survival time distributions of both groups are approximated reasonably well by the Weibull distribution with a shape parameter of 1.00. These proportions assume an enrollment period of 18 months and a follow-up period of 12 months after the last subject is added. In order to allow for a 10% dropout rate, a total of 40 patients will be enrolled. The sample size was calculated using PASS version 14.

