5. STUDY DESIGN

This is a Phase II single-arm open-label study of nivolumab as maintenance therapy after autologous stem cell transplantation in patients with HL at risk of relapse or progression.

Patients will receive nivolumab (240 mg IV) every 2 weeks (± 2 days as long as interval between doses is 12-16 days) starting 45-180 days post-transplant for up to a maximum of 6 months of treatment. To compare immune recovery, a control group of 5 patients will receive standard-of-care procedures and treatment both pre- and post-transplant. Response to treatment for patients receiving study drug will be assessed 6 months and 1 year post-transplant using the Recommendations for Initial Evaluation, Staging, and Response Assessment of Hodgkin and Non-Hodgkin Lymphoma: The Lugano Classification (Cheson et al. 2014, see Appendix F).

The planned enrollment for this study is 40 patients: 35 patients receiving study drug and 5 patients will receive standard-of-care procedures and treatment both pre- and post-transplant.

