5.2 Treatment Duration

Study treatment consists of a maximum of 6 months of treatment. Patients must receive at least 2 cycles of nivolumab to be evaluable for efficacy.

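### Only 35 of the 40 enrolled patients receive nivolumab, so the PFS test cannot have the 36 evaluable patients behind the stated 80.3% power; with the planned 10% dropout, power is about 75%.

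*Combined protocol and SAP*

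**What the plan says.** Section 10.2, repeated in the synopsis under Statistical Methodology, sizes the trial on 12-month PFS, 50% under the null against 70% under the alternative: "A two-sided, one-sample log-rank test calculated from a sample of 36 evaluable subjects achieves 80.3% power at a 0.050 significance level". It gives an event probability of 0.4579 per subject and 16 expected events. It assumes exponential survival (Weibull, shape 1), 18 months of enrolment and 12 months of follow-up after the last patient. It ends: "In order to allow for a 10% dropout rate, a total of 40 patients will be enrolled".

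Section 5 divides the same 40: "The planned enrollment for this study is 40 patients: 35 patients receiving study drug and 5 patients will receive standard-of-care procedures". The synopsis gives the same split. Section 5.4.2 confirms that the 5 controls do not receive nivolumab and are there for the immune-recovery comparison.

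Section 5.2 sets the condition for evaluability: "Patients must receive at least 2 cycles of nivolumab to be evaluable for efficacy". In Section 10.3 the Full Analysis Set (FAS) requires at least one dose of study medication and the efficacy-evaluable set at least two cycles. Section 10.4.2 makes the FAS the main efficacy set and uses the evaluable set for sensitivity analyses.

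**The concern.** The step from 36 to 40 treats every enrolled patient as a nivolumab patient. The split in Section 5 takes the controls out of the 40 rather than adding them to it, and Section 10.2 was not adjusted to match. Section 10.5.1 has the same gap: it times the final analysis to when all enrolled subjects have had two cycles of nivolumab, which the controls never will.

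The PFS calculation is the only justification given for the size of this trial. If the evaluable number is overstated, so is the power. A PFS result that does not reach significance would then be read against a type II error of about 20% when the design, on its own dropout assumption, carries about 25%.

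**Working it through.** **Inputs, all from Section 10.2 unless noted.** 12-month PFS of 50% (null) and 70% (alternative); exponential survival; uniform accrual over 18 months (uniformity is an assumption, supported by the match below) and 12 further months of follow-up; two-sided alpha 0.05; 10% dropout; 35 patients on nivolumab (Section 5).

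**Hazards per month.**
- Null: h0 = −ln(0.50)/12 = 0.05776
- Alternative: h1 = −ln(0.70)/12 = 0.02972
- Hazard ratio: 0.5146

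**Event probability under the alternative.**
p1 = 1 − [exp(−12·h1) − exp(−30·h1)]/(18·h1) = 0.4579. This is the plan's figure. Expected events at 36 patients: 36 × 0.4579 = 16.5 (the plan says 16).

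**Power formula.** The one-sample log-rank test compares observed events O with events E expected under the null hazard. Per patient, under the alternative:
- mean of O: p1 = 0.4579
- mean of E: p0 = p1 × h0/h1 = 0.8898
- standard deviation of O − E, integrated over the accrual pattern: σ = 0.8699

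Power = Φ{[√n · (p0 − p1) − 1.96 · √p0]/σ}, with p0 − p1 = 0.4320 and 1.96 · √p0 = 1.849.

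**The plan's figure first.** At n = 36: (6 × 0.4320 − 1.849)/0.8699 = 0.854, and Φ(0.854) = 0.803. The stated 80.3% is reproduced, and 36/0.9 = 40 reproduces the enrolment total.

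**The same formula at the numbers the design can supply.** Evaluable after dropout: 35 × 0.9 = 31.5.

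| Patients in the test | Expected events | Power |
|---|---|---|
| 36 (as stated) | 16.5 | 80.3% |
| 35 (all treated, no dropout) | 16.0 | 79.2% |
| 32 | 14.7 | 75.3% |
| 31.5 | 14.4 | 74.6% |
| 31 | 14.2 | 73.9% |

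**Simulation.** Trials simulated under the same assumptions and tested with (O − E)/√E reject in 82.4% of runs at n = 36, 81.2% at 35, 77.3% at 32 and 75.8% at 31. The level is about two points higher than the formula gives, but the fall from 36 to 31 or 32 patients is of similar size.

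**Dropout as censoring.** If all 35 treated patients stay in the FAS and dropout is modelled as exponential censoring, the answer depends on when the 10% is reached, which the protocol does not say. Assuming 10% lost by 12 months gives 75.6%; assuming 10% lost by 30 months gives 77.8%.

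**Restoring 36 evaluable patients.** 36/0.9 = 40 treated, plus 5 controls, is 45 enrolled.

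**The case against.** The strongest reply is that 31 to 32 patients is not the population of the main efficacy analysis. That analysis uses the FAS, which needs only one dose, so its planned size is 35. Patients who leave later are censored at their last tumour assessment, not removed. On that reading power is 79.2% with no loss, or 75.6% to 77.8% with dropout as censoring, and about 75% is the pessimistic end. This stands as a reason to report a range. It does not rescue 80.3%, because 35 is still below 36. The plan itself obtained 40 by removing dropouts outright, so applying the same allowance to 35 is a like-for-like comparison.

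A second reply is that the time frame is itself unsettled. The synopsis gives 2 years of enrolment. With 24 + 12 months the formula gives 82.0% at 35 patients and 78.4% at 32. If each patient were instead followed for only 12 months, power at 35 would be about 61%. This is fair: every figure here is conditional on 18 + 12 months. That inconsistency is a separate matter, and it does not account for the 5 controls.

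A third is that safety is the primary objective, PFS is secondary, and Section 10.4.2 does not list the one-sample log-rank test. This limits the consequences: type I error, the PFS estimate and the safety analysis are unaffected. The stated power is still wrong for the design described.

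**Conclusion.** The concern holds. No reading of the current text supplies 36 nivolumab patients to the PFS test: the ceiling is 35 before any dropout, and 31 to 32 after the plan's own 10%. Under the plan's other assumptions (50% against 70% at 12 months, exponential survival, 18 + 12 months, two-sided 0.05), power is 73.9% to 75.3% with dropouts removed and 79.2% if nobody drops out. The overstatement is therefore about 1 to 6.5 percentage points, with about two fewer expected events (14.4 against 16.5) on the plan's dropout assumption. The finding concerns the stated power and evaluable number, not the validity of the test.

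**What to change.** Restate Section 10.2 and the Statistical Methodology part of the synopsis for the design in Section 5:

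- 35 patients receive nivolumab; about 31 to 32 are evaluable after 10% dropout.
- About 14 expected events and about 75% power, with 79% for a 35-patient FAS and no dropout.
- The 5 controls do not contribute to the PFS test.
- The accrual and follow-up periods on which these figures rest. If the 18-month and 2-year enrolment periods are reconciled to something other than 18 + 12 months, recompute with the formula above.

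Section 10.5.1 should refer to treated subjects instead of all enrolled subjects.

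The cost is a text change and a less favourable stated power; no patients are added. If the sponsor prefers to keep 80.3%, the controls must be counted on top of 40 treated patients, which makes 45 enrolled, 5 more than planned.
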